5.7.2.2 Treatment Modifications

Action on study drug (including dose reduction) will be summarized by treatment group, by cycle, and overall.

5.8 Efficacy Analyses

All efficacy evaluations will be conducted using the ITT population unless specified otherwise.

5.8.1 Primary Efficacy Endpoint

The primary endpoint of this study is ORR4 per IRF. ORR4 per IRF is defined as the proportion of patients achieving an objective response that lasts at least 4 months (i.e., duration from first response to last response is ≥ 4 months) on study as determined by an IRF. Patients whose first response occurs after the start of subsequent anti-cancer therapy but otherwise meet the primary endpoint criteria will be excluded. For objective response, a patient must achieve a CR or PR. The objective response will be considered maintained for patients with a previous CR who experience recurrent disease (i.e. Relapse) unless the criteria for progressive disease are met. Determination of objective response will be based on a GRS, which consists of skin evaluation (mSWAT assessment) by investigator, nodal and visceral radiographic assessment by IRF, and detection of circulating Sézary cells (MF only) by IRF. Skin evaluation is done at screening, before dosing on Day 1 of Cycles 1, 2, and 3, at the end of every cycle beginning at Cycle 3, EOT, and at post treatment follow-up visits. Radiographic and blood assessments are less frequent due to ethical and logistical considerations.

For patients without nodal or visceral involvement (as determined by baseline CT scans), CT scans will be performed at screening and:

- During the cycle following the first skin response, ideally corresponding to the confirmation of the skin response, and 6 cycles (a minimum or 4 months) after that confirmed skin response.
- If there is a question of new or progressive disease in the LN/viscera

For patients with baseline nodal/visceral disease, CT scans will be performed at screening and:

- At the end of Cycles 3, 6, 9, 12, and 15, and per the follow-up schedule until disease progression
- If there is a question of new or progressive disease in the LN/viscera
- At EOT if the previous CT scan was performed more than 8 weeks before EOT

A blood sample for Sézary cell enumeration in patients with MF will be collected at screening; at the end of Cycles 3, 6, 9, 12, and 15, at EOT, and per the follow-up schedule until progressive disease or study closure.

GRS will be determined by IRF at the end of each cycle beginning at Cycle 3, EOT, and at post treatment follow-up visits until disease progression, death or study closure. The GRS assessment at each cycle will incorporate the skin response at that cycle as well as the most recent nodal, visceral, and blood responses prior to or at the time of the GRS assessment time point. CR or PR per GRS will be confirmed by sustained response in skin per mSWAT assessment at the subsequent cycle.

For patients with skin only disease at baseline, GRS is essentially determined by skin response because disease progression in node/viscera/blood is atypical in the presence of a continuing skin response. In addition, the primary endpoint is further supported by CT confirmation of continued nodal/visceral noninvolvement at the cycle after the first skin response and 6 cycles after the first confirmed skin response. For patients with baseline nodal/viscera/blood involvement, GRS assessment at each cycle will incorporate the skin response at that cycle as well as nodal, visceral, and blood responses based upon the most recent respective compartment assessments prior to the GRS assessment time point. Blood results should be within 3 cycles. The CT scans should also be within 3 cycles for patients with nodal/viscera involvement.

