Figure 7-1 mSWAT % Total Body Surface Area (TBSA) for 12 Main Body Areas

[figure not shown]

Table 7-2 Response in Skin

Response	Definition
Complete response (CR)	100% clearance of skin lesions ^a
Partial response (PR)	50%-99% clearance of skin disease from baseline No new tumors in patients without tumors at baseline (MF) No new tumors (pcALCL)
Stable disease (SD)	< 25% increase to < 50% clearance in skin disease from baseline No new tumors in patients without tumors at baseline (MF)
Progressive disease (PD) ^b	≥ 25% increase in skin disease from baseline, or Loss of response: in those with CR or PR, increase of skin score of greater than the sum of nadir plus 50% baseline score, or New tumors in patients without tumors at baseline (MF)
Relapse	Any disease recurrence in those with complete response

Response criteria for MF are per Olsen 2011,⁽⁴⁾ and for pcALCL per Kempf 2011.⁽¹⁾

Abbreviations: CR = complete response; PR = partial response; SD = stable disease; PD = progressive disease.

a A biopsy of normal appearing skin is unnecessary to assign a complete response. However, a skin biopsy should be performed on a representative area of the skin if there is any question of residual disease (persistent erythema or pigmentary change) where otherwise a complete response would exist. If histologic features are suspicious or suggestive of mycosis fungoides/Sézary syndrome, the response should be considered a partial response only.

b Whichever criterion occurs first.

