7.4.17.2 Lymph Node and Visceral Evaluation

Lymph nodes and visceral involvement will be assessed by CT scan, and responses are defined in [Table 7-3](#) and [Table 7-4](#).

Table 7-3 Response in Lymph Nodes^a

Response	Definition
CR	All lymph nodes are now ≤ 1.5 cm ^b in greatest transverse (long axis) diameter by method used to assess lymph nodes at baseline or biopsy negative for lymphoma. In addition, lymph nodes that show lymphoma involvement by biopsy ^c and ≤ 1.5 cm ^b in long axis diameter and > 1 cm in short axis at baseline, must now be ≤ 1 cm in diameter of the short axis or biopsy negative for lymphoma
PR	Cumulative reduction $\geq 50\%$ of the SPD of each abnormal lymph node at baseline and no new lymph node > 1.5 cm ^b in the diameter of the long axis or > 1.0 cm in the short axis if the long axis is 1-1.5 cm diameter
SD	Fails to attain the criteria for CR, PR, and PD
PD ^d	(1) $\geq 50\%$ increase in SPD from baseline of lymph nodes, or (2) Any new node > 1.5 cm ^b in greatest transverse diameter or > 1 cm in the short axis diameter if 1-1.5 cm in long axis that is proven to be lymphoma histologically ^c , or (3) Loss of response: in those with PR (or CR if pcALCL), $> 50\%$ increase from nadir in SPD of lymph nodes
Relapse	Any new lymph node > 1.5 cm ^b in the long axis diameter: In those with CR (pcALCL) In those with CR proven to be lymphoma histologically ^c (MF)

Response criteria are per Olsen 2011,⁽⁶³⁾ Kempf 2011,⁽¹¹⁾ and Cheson 2007.⁽⁶⁴⁾

Abbreviations: CR = complete response; PR = partial response; SPD = sum of the maximum linear dimension (major axis) X longest perpendicular dimension (minor axis); SD = stable disease; PD = progressive disease.

a Peripheral and central lymph nodes.

b Response criteria are similar for patients with MF and pcALCL. However, per the EORTC, ISCL and USCLC consensus recommendations for the treatment of non-MF primary cutaneous CD30-positive lymphoproliferative disorders,⁽¹¹⁾ an abnormal lymph node is considered ≥ 1.5 cm and should be considered when assessing nodal response in patient with pcALCL.

c For patients with MF, lymphoma involvement is defined as N3 (ie, partial or complete effacement of lymph node architecture by atypical or frankly neoplastic cells)

d Whichever criterion occurs first.

Table 7-4 Response in Viscera

Response	Definition

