7.4.17.4 Global Response Score

Global response score (GRS) is an assessment whereby each component of the TNM(B) staging (skin, nodes, viscera, and blood for MF), has been given its own definition of response. Due to the primacy of the response in the skin in CTCL, no patient with a global objective response should have less than a PR in the skin. The global response score definition is provided in [Table 7-6](#).

Response to treatment (CR, PR, SD, PD, relapse) will be monitored on a continual basis. For all treated patients, GRS will be assessed at the end of Cycles 3, 6, 9, 12, and 15 (Days 16-21 or before dosing on Day 1 of the subsequent cycle); at EOT; and then every 12 weeks for a minimum of 24 months, and then every 6 months; or until disease progression or study closure. GRS will be determined based upon the most recent disease assessments for each component (mSWAT, CT scans, Sezary cell count for MF patients). For patients without baseline nodal/visceral involvement, the schedule for obtaining CT scans will likely not correlate with the timing of GRS determinations; thus, the nodal/visceral response

Brentuximab vedotin (SGN-35)

Clinical Study Protocol C25001 Amendment 5, EudraCT: 2010-024215-14

component should be based upon the most recent CT scan findings prior to the GRS assessment time point. Additional unscheduled GRS determinations may occur following a change in response in skin or at the time of a CT scan. Relapse will be categorized in the study endpoints definition as recurrent disease in patients with complete response.

Table 7-6 Global Response Score

Global Score	Definition	Skin	Nodes	Blood	Viscera
CR	Complete disappearance of all clinical evidence of disease	CR	All categories have CR/NI		
PR	Regression of measurable disease	CR	All categories do not have a CR/NI and no category has a PD		
		PR	No category has a PD and if any other category involved at baseline, at least one has a CR or PR		
SD	Failure to attain CR, PR or PD representative of all disease	PR	No category has a PD and if any other category involved at baseline, no CR or PR in any		
		SD	CR/NI,PR,SD in any category and no category has a PD		
PD	Progressive disease		PD in any category		
Relapse	Recurrence disease in prior CR		Relapse in any category		

Abbreviations: CR = complete response; NI = noninvolved; PR = partial response; PD = progressive disease; SD = stable disease.

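### For pcALCL, the SAP's relapse rule keeps an ORR4 response running after a new skin tumour that takes the patient below the protocol's skin-PR floor without reaching PD

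*SAP*

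**What the plan says.** SAP 5.8.1 defines ORR4 by time in response: the "duration from first response to last response is" at least 4 months. It then says how relapse after CR is handled: "The objective response will be considered maintained for patients with a previous CR who experience recurrent disease (i.e. Relapse"). With its qualification, response continues through "recurrent disease (i.e. Relapse) unless the criteria for progressive disease are met".

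The categories this rule depends on are in the protocol:

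- **Table 7-2, skin PR:** 50% to 99% clearance from baseline, with the added condition "No new tumors (pcALCL").
- **Table 7-2, skin PD:** a rise of at least 25% over baseline; or, after CR or PR, an "increase of skin score of greater than the sum of nadir plus 50% baseline score"; or "new tumors in patients without tumors at baseline (MF"). There is no new-tumour criterion for pcALCL.
- **Table 7-2, relapse:** any recurrence after CR.
- **Table 7-6:** Relapse ("Recurrence disease in prior CR") has its own row, apart from CR, PR, SD and PD.
- **Section 7.4.17.4, text above Table 7-6:** because skin response has primacy in CTCL, a patient cannot be a global objective responder with a skin response worse than PR.

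SAP Section 6 declares no changes from the protocol's planned analyses.

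**The concern.** The SAP rule is harmless if every relapse short of PD is still at PR level. The response would then simply have dropped from CR to PR. The question is whether the tables guarantee this in both diagnoses. If they do not, some visits that fail the protocol's own test of objective response would count towards the 4 months required by the primary endpoint. The pcALCL subgroup analysis in SAP 5.8.1.2 would be affected in the same way. No sensitivity analysis in SAP 5.8.1.1 or 5.8.1.2 is stated to end response at relapse, so the reported results would not show how much depends on the rule.

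**Working it through.** **1. Skin thresholds after CR.** Let B be the baseline mSWAT score and S the current score. After CR the nadir is 0.

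- Loss-of-response PD: S > nadir + 0.5B = 0.5B.
- Clearance = 1 − S/B. The PR minimum of 50% clearance means S ≤ 0.5B.

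On score alone the two rules meet exactly at 0.5B: a relapse short of PD has at least 50% clearance. Any mismatch must come from the new-tumour conditions.

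**2. Worked cases.** B = 20 is assumed for illustration.

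| Relapse after CR | S | Clearance | Skin PD | Skin PR | SAP 5.8.1 |
|---|---|---|---|---|---|
| pcALCL, new tumour | 1 | 95% | no | no | maintained |
| pcALCL, new tumour | 4 | 80% | no | no | maintained |
| pcALCL, new tumour | 8 | 60% | no | no | maintained |
| pcALCL, new tumour | 10 | 50% | no | no | maintained |
| pcALCL, new tumour | 10.1 | 49.5% | yes | no | ended |
| pcALCL, regrowth, no new tumour | 4 | 80% | no | yes | maintained |
| MF with baseline tumours, new tumour | 4 | 80% | no | yes | maintained |
| MF without baseline tumours, new tumour | 4 | 80% | yes | no | ended |

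For MF, and for pcALCL regrowth without a new tumour, the SAP rule agrees with the skin-PR floor. The mismatch is confined to pcALCL with a new skin tumour and S ≤ 0.5B.

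**3. When ORR4 status changes.** All of the following must hold: the diagnosis is pcALCL; the patient reached CR; the relapse came before 4 months of response; it was a new tumour rather than regrowth; and PD was not reached by 4 months. A response already held for 4 months qualifies under either rule.

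**4. Size per patient.** The denominator is the planned 62 per arm. It reproduces from the stated inputs (70% vs 40%, two-sided α = 0.05, 90% power, χ² test without continuity correction):

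n = [1.960·√(2·0.55·0.45) + 1.282·√(0.70·0.30 + 0.40·0.60)]² / 0.30² = 55.7, so 56 per arm.

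The 10% dropout allowance gives 56 × 1.10 = 61.6, so 62 per arm and 124 in total. Dividing by 0.90 instead gives 63 per arm. The sample size is not at issue.

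- One patient: 1/62 = 1.6 points on an arm's ORR4.
- One patient in a pcALCL stratum of the minimum size, 15 per arm: 1/15 = 6.7 points on that stratum's rate.
- Assumed 1 to 4 patients, all in one arm: 1/62 to 4/62 = 1.6 to 6.5 points on the difference.
- Equal numbers in both arms of 62: no change in the difference.

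The pcALCL minimum is 30 of 124 (24%). That is the group in which the case can arise, not the share affected. The documents give no rate for the event.

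**The case against.** The strongest reply is that the protocol never says relapse ends an ORR4 response. It keeps Relapse separate from PD as well as from CR and PR, and ends duration of response at progression (Protocol 8.1.6.2; SAP 5.8.3 agrees). The SAP openly prespecifies how to treat a category the protocol leaves open, so another rule might be only a preference. Part of this stands: no explicit protocol rule on relapse and ORR4 is broken. But the skin-PR minimum in Section 7.4.17.4 is explicit, and the pcALCL new-tumour visit fails it. The conflict is with that sentence.

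A reader might infer more than the documents support:

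- **Nodes.** For pcALCL, Table 7-3 defines relapse as "Any new lymph node > 1.5 cm" in long axis after CR, without histology, so nodes might seem to have the same gap. They do not in general. A histologically proven new node is PD, and the loss-of-response criterion (SPD more than 50% above nadir) extends to CR in pcALCL with no histology requirement. Table 7-6 also makes skin CR with a node that is neither CR nor PD a global PR, so the skin floor is not breached. Table 7-3 does not say whether a new node enters the SPD, but that does not establish the same conflict.
- **Direction.** Only patients with a prior CR get the credit, but this does not show that it favours the arm with more CRs. What matters is early new-tumour relapse after CR, and no rate is given for either arm.
- **Duration of response.** Both documents define it to PD, so ending it at relapse would contradict them.

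It is also fair to say that pcALCL with at least 50% clearance and a new tumour, but no prior CR, lies outside the SAP rule. Table 7-2 gives that patient no row. The residual wording of global SD in Table 7-6 points to a category, but the skin combinations listed there do not include this one.

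**Conclusion.** The concern holds for one defined case: a pcALCL patient who relapses from CR with a new skin tumour and a skin score at or below 50% of baseline. SAP 5.8.1 counts that patient as still responding, although the skin is below PR and Protocol 7.4.17.4 makes skin PR the minimum for a global objective response. The classification follows from the tables alone. The effect on ORR4 depends on how often such relapses occur before 4 months without PD by 4 months, which the documents do not say. It is 1.6 points per patient in an arm of 62, or 1.6 to 6.5 points if 1 to 4 patients in one arm only are assumed. The direction is unknown. No claim about nodes, or that one arm is favoured, is supported.

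**What to change.** - **Preferred.** In SAP 5.8.1, count response as maintained after relapse only while the skin still meets CR or PR under Table 7-2 (for pcALCL, no new tumour), in line with Protocol 7.4.17.4. Report ORR4 under the current rule as a sensitivity analysis.
- **Minimum.** Keep the current rule and add a prespecified ORR4 sensitivity analysis that ends response at the first relapse failing skin PR.
- **Either way.** Reconcile Table 7-2 so that pcALCL with at least 50% clearance plus a new tumour has a category. This clarifies the protocol's response criteria, so it goes beyond SAP wording. Settle it before database lock.
- **Leave alone.** Duration of response stays as defined, to PD. Under the preferred rule a few patients could fail ORR4 with a duration of response beyond 4 months; a table footnote should say so.

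The cost is a sentence in the SAP, one table clarification and one extra analysis. The downside is that ORR4 may be slightly lower.

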5.8.1.1 Primary Efficacy Analysis

The primary endpoint, ORR4 per IRF, will be analyzed using a Cochran-Mantel-Haenszel test stratified by baseline disease diagnosis (pcALCL or MF) based on the ITT population.

The 95% confidence interval (CI) of the difference in ORR4 between the 2 treatments will be provided. No imputation will be conducted for missing data. Patients who do not have any post baseline response assessment as specified in the protocol, or patients who have no response before dropout, will be counted as nonresponders.

Sensitivity analyses will be performed for ORR per IRF in the study as well as ORR4 per IRF defined by the response criteria used for Romidepsin approval and published by Whittaker 2010. Analysis for ORR4 per IRF defined by the response criteria used for Romidepsin approval will also be performed for MF patients only. Sensitivity analyses will be performed for ORR and ORR4 based on investigator's GRS assessment as well.

Another sensitivity analysis will be conducted for ORR4 per IRF in the ITT population to assess the robustness of the primary analysis's use of most recently available CT scans and blood assessments for GRS. For patients with baseline nodal/visceral/blood disease, the sensitivity analysis will only use GRS assessed at time points with concurrent nodal/viscera/blood component assessments as specified in the protocol SOE while for patients with skin-only disease, the analysis will use the same GRS assessment frequency as the primary analysis.

5.8.1.2 Other Analysis

The same analysis on ORR4 per IRF using a Cochran-Mantel-Haenszel test stratified by baseline disease diagnosis (pcALCL and MF) will be performed for the All-Enrolled population, Response-Evaluable population, as well as the PP population. The 95% CI of the difference in ORR4 between the 2 treatments will be provided. No imputation will be conducted for missing data. Patients who do not have any post baseline response assessment as specified in the protocol, or patients who have no response before dropout, will be counted as nonresponders.

Similarly, analyses will also be performed for the primary endpoint on, but not limited to, the following subgroups (with at least 10 patients in each subgroup per treatment arm), as applicable:

Subgroup	Group Definition
Baseline disease diagnosis	MF, pcALCL
ECOG performance status	0, 1, 2
Gender	Female, male
Age	< 65 years, ≥ 65 years
Region	North America, Europe, Asia, and rest of world
Race	White, nonwhite
Physician's choice (bexarotene)	Brentuximab vedotin vs bexarotene
Physician's choice (MTX)	Brentuximab vedotin vs MTX

Concordance between the IRF and investigator's GRS assessment for ORR4 will be assessed by percent positive, negative, and overall agreement.

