4. STUDY DESIGN

4.1 Overview of Study Design

This is an open-label, randomized, multicenter study. All patients must have a diagnosis of MF or pcALCL and histologically-confirmed CD30+ disease by central laboratory assessment and pathology review. Patients are to be stratified by diagnosis: pcALCL or MF. Patients will enter 1 of 2 treatment arms:

- **Arm 1:** brentuximab vedotin monotherapy

Brentuximab vedotin (1.8 mg/kg) will be administered intravenously over approximately 30 minutes once every 21 days and may continue as monotherapy for up to a total of 16 cycles (48 weeks).

Brentuximab vedotin (SGN-35)

Clinical Study Protocol C25001 Amendment 5, EudraCT: 2010-024215-14

- **Arm 2:** methotrexate (MTX) or bexarotene per physician's choice, up to a total of 48 weeks treatment.

Methotrexate will be administered orally (5 to 50 mg) once weekly. Dose adjustment is guided by patient response and toxicity.

OR

Bexarotene will be administered orally (300 mg/m² recommended total dose per guidelines in [Figure 6-1](#)) once daily with meals.

Investigators are advised to consider a patient's prior treatment with reference therapy. It is recommended that patients who were last treated with methotrexate be treated with bexarotene, and patients who last received bexarotene be treated with methotrexate.

Objective response, lasting at least 4 months (ORR4), per independent review facility (IRF), will be assessed by global response score (GRS), which consists of skin evaluation (mSWAT assessment), nodal and visceral radiographic assessment, and detection of circulating Sézary cells (MF only). Objective response will be evaluated at the end of Cycles 3, 6, 9, 12, and 15, and at end of treatment (EOT). All treated patients without disease progression at EOT/ET will then be followed for objective response every 12 weeks for a minimum of 24 months, and then every 6 months; or until disease progression or study closure. CR or PR per GRS will be confirmed by sustained response in skin per mSWAT assessment at the subsequent cycle. Additional unscheduled GRS determinations may occur following a change in response in skin or at the time of a CT scan.

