15. Oral retinoid therapy for any indication within 3 weeks of the first dose of study drug.
16. Systemic therapy with Vitamin A in doses of greater than 15,000 IU (5,000 mcg) per day (equivalent to approximately 3 times RDA) within 3 weeks before the first dose of study drug.

Brentuximab vedotin (SGN-35)

Clinical Study Protocol C25001 Amendment 5, EudraCT: 2010-024215-14

17. History of pancreatitis or significant risk factors for developing pancreatitis (eg, prior pancreatitis, uncontrolled hyperlipidemia, excessive alcohol consumption, uncontrolled diabetes mellitus, biliary tract disease, and medications known to increase triglyceride levels or to be associated with pancreatic toxicity), or elevated lipase value $\geq 3 \times$ ULN with an amylase level $>$ ULN at screening.
18. Any other condition that, in the opinion of the investigator or project clinician, would interfere with a patient's ability to receive or complete the study.
19. Previous receipt of brentuximab vedotin.

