6.2.2 Bexarotene

The risks of bexarotene therapy should be considered by the investigator when selecting an appropriate Arm B treatment. The recommended total dose of bexarotene capsules is 300 mg/m²/day. The Mosteller formula or the Dubois and Dubois formula should be used for all body surface area (BSA) determinations for each patient, and are provided in Section 15.2. Dosage should be rounded to the nearest 75 mg. Bexarotene capsules should be taken as a single oral daily dose with a meal. The dose of bexarotene may be reduced to 200 mg/m²/day PO then to 100 mg/m²/day PO, or temporarily suspended, if clinical toxicity occurs. When toxicity is controlled, doses may be restarted and carefully increased. Bexarotene capsules should be continued as long as the patient is deriving benefit, up to 48 weeks. For further dose modification guidelines, refer to the bexarotene product label.

Further Guidelines for Bexarotene Use

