Hypertriglyceridemia of all grades has been recorded in 79% of patients who took bexarotene in a study in early-stage CTCL; hypercholesterolemia occurred in 48% of patients; and hypothyroidism in 40%. Similarly, in a study in advanced-stage CTCL, the incidence of hyperlipidemia of all grades (primarily hypertriglyceridemia) with bexarotene was 82%, hypercholesterolemia was 30%, and hypothyroidism was 29%. Before initiating bexarotene therapy, a patient history should be taken to identify those with familial hypertriglyceridemia, uncorrected hypothyroidism, an individual or family history of myocardial infarction or cardiovascular events, or a history of diabetes. A minority of patients with familial hypertriglyceridemia cannot tolerate bexarotene and should be considered for alternative therapy. A substantial proportion of patients will have pathology related to cardiovascular atherosclerosis or a history of cardiovascular disease and have hypertriglyceridemia that will need to be treated before bexarotene therapy. In addition, those with coronary heart disease are likely to have active atherosclerotic plaques that should be stabilized with low-dose statin therapy (eg, 10 mg daily) 3 days before beginning bexarotene. Diabetes can also contribute to the development of coronary heart disease and should be controlled. These groups of at-risk patients are identified by elevated plasma lipid levels and should be monitored particularly closely during treatment, with measurement of fasting lipid levels at weekly intervals for as long as necessary until it becomes apparent that these are stabilized reliably at the levels recommended.

Prior to dosing with bexarotene, attempts should be made to obtain triglyceride levels that meet the normalized lipid levels per the United States Prescribing Information (USPI)

Brentuximab vedotin (SGN-35)**Clinical Study Protocol C25001 Amendment 5, EudraCT: 2010-024215-14**

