7.4.13 Enrollment

A patient is considered to be enrolled in the study when randomized to a treatment arm.

Procedures for completion of the enrollment information are described in the Study Manual.

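### Must SAP 5.8.1.2 define which brentuximab vedotin patients enter the rows against bexarotene and against methotrexate?

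*SAP*

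**What the plan says.** SAP 5.8.1.2 repeats the primary-endpoint analysis (ORR4, objective response lasting at least 4 months) in eight subgroup rows. Six are baseline traits that place patients in both arms: diagnosis, ECOG status, gender, age, region and race. The other two are titled by the physician's choice, and their group definitions read "Brentuximab vedotin vs bexarotene" and "Brentuximab vedotin vs MTX". A general size rule covers all eight rows: "with at least 10 patients in each subgroup per treatment arm".

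The control drug is the investigator's decision. Protocol 4.1 ties it to the last reference therapy: "It is recommended that patients who were last treated with methotrexate be treated with bexarotene". The converse applies after bexarotene. Protocol 6.2.2 adds a risk consideration: "The risks of bexarotene therapy should be considered by the investigator when selecting an appropriate Arm B treatment". It also says: "A minority of patients with familial hypertriglyceridemia cannot tolerate bexarotene and should be considered for alternative therapy".

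Randomisation is stratified by diagnosis only (Protocol 8.1.2, SAP 5.2). Neither document says whether the intended control drug is recorded before randomisation. Protocol 7.4.13 leaves the details elsewhere: "Procedures for completion of the enrollment information are described in the Study Manual".

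**The concern.** A subgroup comparison keeps the protection of randomisation only if membership is fixed before randomisation and applied alike in both arms. These two rows are defined by something observed in the control arm alone. If the whole brentuximab arm is used, each row compares all randomised brentuximab patients with the controls whose investigator picked one particular drug. If the features behind that pick also predict response, the difference mixes drug effect with patient selection. Stratifying the Cochran-Mantel-Haenszel test by diagnosis removes only the part that runs through diagnosis.

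A second gap is whether controls are placed by drug chosen or drug received. Analysing by randomised treatment does not settle this, because controls are randomised to physician's choice and not to a named drug.

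These rows are also the only efficacy comparisons with each comparator that the SAP specifies, and readers will look at them. Protocol 1.4.2 cites a 45% response rate for bexarotene at the 300 mg/m²/day dose and 20 of 60 (33%) for methotrexate in T2 disease.

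**Working it through.** **The plan's own figure.** Inputs from Protocol 8.1.1 and SAP 5.1: ORR4 of 70% and 40%, two-sided α = 0.05, power 90%, dropout 10%.

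n per arm = [1.96·√(2·0.55·0.45) + 1.282·√(0.7·0.3 + 0.4·0.6)]² / 0.30² = 55.7, so 56. Dropout as 56 × 1.1 gives 62 per arm (124 in total); as 56 / 0.9 it gives 63 (126 in total). The stated 124 reproduces, and nothing below alters it.

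**Bias on the whole-arm reading.** Let s be the share of patients who would be given bexarotene. Let Rb and Rm be brentuximab ORR4 in would-be-bexarotene and would-be-methotrexate patients, and d = Rm − Rb. The whole arm shows s·Rb + (1 − s)·Rm. Hence:

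- Bexarotene row: bias = s·Rb + (1 − s)·Rm − Rb = (1 − s)·d
- Methotrexate row: bias = s·Rb + (1 − s)·Rm − Rm = −s·d

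The documents give neither s nor d. With assumed s = 0.3 to 0.7 and d = 10 points:

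| s | bexarotene row | methotrexate row | coverage of nominal 95% CI, bexarotene row |
|---|---|---|---|
| 0.3 | +7.0 | −3.0 | 91.4% |
| 0.5 | +5.0 | −5.0 | 92.4% |
| 0.7 | +3.0 | −7.0 | 93.8% |

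Coverage is Φ(1.96 − b/SE) − Φ(−1.96 − b/SE), where b is the bias and SE the whole-arm standard error used in the next step. At d = 0 the bias is zero and coverage is 95%. A 3-point bias, one tenth of the planned 30-point effect, needs d = 3/0.5 = 6 at s = 0.5.

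Stronger assumptions give more. Suppose no drug effect, a prognostic factor present in half the patients, and overall ORR4 of 40%. Response is 50% and 30% by prognosis, and bexarotene is chosen with probability 0.6 and 0.4. Bexarotene controls then respond at (0.5·0.6·0.5 + 0.5·0.4·0.3)/0.5 = 42%, a spurious −2 points. With response of 60% and 20% and choice probabilities of 0.8 and 0.2, they respond at (0.5·0.8·0.6 + 0.5·0.2·0.2)/0.5 = 52%, a spurious −12 points. The methotrexate row mirrors these at +2 and +12. The size is set by the assumptions and not by anything in the plan.

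**What the documents say about d.** Protocol 1.4.3 holds that earlier systemic treatments are not usually thought to change sensitivity to the next one, which argues for a small d through the last-therapy route. Exclusion 17 narrows the lipid route by removing from both arms patients with, among other things, "uncontrolled hyperlipidemia, excessive alcohol consumption, uncontrolled diabetes mellitus, biliary tract disease, and medications known to increase triglyceride levels". No passage links bexarotene risk to ORR4.

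**Cost of splitting both arms.** Half-width = 1.96·√(0.7·0.3/nBV + 0.4·0.6/nC), unstratified, with nC = 62·s rounded. nBV is 62 for the whole arm and equals nC when both arms are split. Figures are for the bexarotene row; the methotrexate row mirrors them.

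| s | nC | half-width, whole arm | half-width, both split | power, whole arm | power, both split |
|---|---|---|---|---|---|
| 0.3 | 19 | 24.8 | 30.2 | 66% | 46% |
| 0.5 | 31 | 20.7 | 23.6 | 80% | 67% |
| 0.7 | 43 | 18.6 | 20.1 | 87% | 81% |

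With both arms split, the size rule binds in both. Both rows are reportable only if the bexarotene share lies between 10/62 = 16.1% and 52/62 = 83.9% in each arm.

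**The case for a change.** The best case for acting is that the gap is real and cheap to close. The size rule sets a number and does not define membership. The protocol contains no subgroup definition. An unstated construction leaves room to choose after the data are seen. One sentence could state the construction and label the rows non-randomised, and a baseline table by control drug could be built from prior therapies already collected under Protocol 7.4.3.

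Part of this stands. The definition is missing, and a whole-arm comparison is not randomised. But the choice is less open than it looks. The row labels point to the whole brentuximab arm, and the other reading needs each brentuximab patient's intended control drug, which neither document mentions. Such a record might exist in the Study Manual or the IVRS/IWRS, since a field can be captured without being a stratum. Its absence therefore cannot be asserted, and a remedy cannot be built on its presence. If it does not exist, adding it by amendment helps only patients not yet randomised. A label and a table would make the selection more visible but would not remove it, and the row titles already name the physician's choice.

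The drug-received variant adds little. If 6 of 62 controls were undosed nonresponders and fell out of both rows, control ORR4 over the two rows would be 24.8/56 = 44.3% instead of 40%, which works against brentuximab. The 6 has no source in the documents. Dropping randomised controls would also sit badly with the ITT default in SAP 5.8 and the nonresponder rule in 5.8.1.2.

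**Conclusion.** No change to the plan. This is an unwritten definition in a supplementary table, and an analyst can fill it sensibly: use the whole brentuximab arm in both rows, place controls by the drug chosen so that undosed patients keep their row, and read both rows as descriptive. SAP 3.2 rests the efficacy conclusion on the primary analysis in 5.8.1.1. SAP 3.1 and 3.2 confine the error-controlled hypotheses to ORR4, complete response rate, PFS and the Skindex-29 symptom domain. Neither subgroup row feeds any of these.

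The alternative construction is a trade-off: comparability in exchange for precision, and it depends on data not shown to exist. Under the assumed shares it adds 1.5 points (20.1 − 18.6) to 5.4 points (30.2 − 24.8) to the half-width in the bexarotene row. The bias it would remove is unknown and may be zero. It is 0 to 7 points with s = 0.3 to 0.7 and d = 0 to 10, and as much as 12 under the strongest selection tried; all these inputs are assumptions. The conclusion rests on the rows remaining supplementary. A comparative claim against one control drug drawn from them would need the selection addressed first.
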